#### **4.4.2            Prohibited Therapy**

A listing of concomitant medications and foods that are prohibited or should be used with caution due to potential PK drug-drug interactions is provided in [Appendix 19](#). Biologic response modifiers and disease-modifying antirheumatic drugs (DMARDs) other than those mentioned above are not allowed during this study and any use will require discontinuation of study treatment.

Specifically, the use of the following therapies is prohibited in conjunction with study drug treatment:

- All biosimilar and biological agents (e.g., TNF inhibitors, IL-17, IL-12/23, abatacept, denosumab) as well as biosimilars (investigational or approved)
- Anti-CD20 monoclonal antibody
- Belimumab (Benlysta)
- Chlorambucil
- Cyclophosphamide
- Heparin, low molecular weight heparin, and other injectable systemic anticoagulants
- Immunosorbent column
- Investigational therapy other than study drug
- IV Ig
- Oral anticoagulants, including but not limited to warfarin, dabigatran, rivaroxaban, and apixaban
- Sirolimus
- Systemic calcineurin inhibitors (e.g., tacrolimus, cyclosporine)
- Tocilizumab and other anti-IL6R or anti-IL6 agents
- Tofacitinib and other JAK inhibitors
- *IV or IM steroids at doses greater than 40 mg prednisone PO or equivalent with the exception of use as escape therapy*

Please see [Appendix 19](#) for additional prohibited therapies during this study.

##### **4.4.2.1            Live or Attenuated Vaccinations**

Immunization with a live or attenuated vaccine is prohibited within 6 weeks prior to randomization and for the duration of study participation, including the 8-week follow-up period after the administration of the last dose. See Section [5.1.1.2](#) for further details and precautions around vaccinations.

#### **4.4.2.2 CYP3A and BCRP-Mediated Drug Interactions**

*Preliminary data from a clinical drug-drug interaction study (Study GP39616) suggest that GDC-0853 may be classified as a mild inhibitor of CYP3A at clinically relevant doses. It is possible that GDC-0853 inhibition of CYP3A may alter the metabolism of CYP3A substrates and result in increased plasma concentrations of CYP3A substrates.*

Therefore, medications in the following categories (listed in detail in [Appendix 19](#)) should be used with caution in consultation with the Medical Monitor (or delegate) as necessary unless otherwise specified in Section 4.4.2:

- Sensitive CYP3A substrates
- CYP3A substrates with a narrow therapeutic index

*The use of hormone-replacement therapy or hormonal contraceptives containing the CYP3A substrate ethinylestradiol (with the concomitant use of a barrier method) is permitted; however, patients should be counseled regarding the potential risks and benefit of these medications per the local prescribing information. Any increase in ethinylestradiol plasma concentrations is anticipated to be modest at most due to the relatively minor contribution of CYP-mediated oxidation in the clearance of orally administered ethinylestradiol (Zhang et al. 2007); however, increased ethinylestradiol plasma concentrations may lead to an increase in common side effects (e.g. nausea, breast tenderness, and headaches) and a theoretical increase in rare dose-related events (e.g. thromboembolism; Inman et al. 1970).*

*Preliminary data from Study GP39616 also suggest that GDC-0853 may be classified as a moderately sensitive substrate of CYP3A at clinically relevant doses. There is a moderate potential for a drug-drug interaction with any medication that strongly inhibits or induces this enzyme. Therefore, medications in the following categories (listed in detail in [Appendix 19](#)) should be avoided for 7 days or 5 half-lives, whichever is longer, prior to the first dose of study drug until the last dose of study drug, unless otherwise advised by the Medical Monitor (or delegate). If use of one of these medications is necessary, the risks and benefits should be discussed with the Medical Monitor prior to concomitant administration with study drug.*

- Strong CYP3A inhibitors
- Moderate or strong CYP3A inducers

*Lastly, preliminary data from Study GP39616 suggest that GDC-0853 is a moderate inhibitor of the breast cancer resistance protein (BCRP) (also known as ABCG2) transporter protein at clinically relevant doses. There is a potential for increased plasma concentrations of drugs known to be substrates of the BCRP transporter. Plasma concentrations of the medications in the following category (listed in detail in [Appendix 19](#)) may increase; therefore, they should be used with caution in consultation*

with the Medical Monitor (or delegate) as necessary unless otherwise specified in Section 4.4.2:

- BCRP substrates with a narrow therapeutic index

The medications listed in [Appendix 19](#) are not necessarily comprehensive. Thus, the investigator should consult the prescribing information for concomitant medications as well as the Internet references provided below when determining whether a certain medication is metabolized by or strongly inhibits or induces CYP3A or is a sensitive substrate of BCRP. The investigator should contact the Medical Monitor if questions arise regarding medications that may interact with CYP3A or BCRP.

<https://www.fda.gov/Drugs/DevelopmentApprovalProcess/DevelopmentResources/DrugInteractionsLabeling/ucm093664.htm> (Tables 3-1, 3-2, 3-3, and 5-1)

<http://medicine.iupui.edu/clinpharm/ddis/table.aspx>

#### **4.4.3 Prohibited Food**

Use of the following foods is prohibited during the study and for at least 7 days prior to initiation of study treatment due to their effects on the cytochrome P450 3A4 enzyme, which is involved in GDC-0853 metabolism: furanocoumarin derivatives as found in grapefruit, Seville orange, pomegranate, or star fruit juice or products. Please refer to [Appendix 19](#) for additional information.

#### **4.4.4 Additional Restrictions**

Patients should be fasting for  $\geq 4$  hours prior to pre-dose PK draws at Day 1 and Week 24, and also when fasting lipids are drawn (Day 1, Week 12, Week 24, Week 36, and Week 48). At Week 24, patients should also remain fasting for the 2-hour PK timepoint (see [Appendix 1](#) and [Appendix 2](#)). The morning dose of oral study drug will be administered at the strongly recommended morning clinic visit while fasting.

### **4.5 STUDY ASSESSMENTS**

Please see [Appendix 1](#) and [Appendix 2](#) for the schedule of activities to be performed during the study.

The screening visit can occur up to 35 days prior to the first dose of study drug. The screening period may be extended upon the approval of the Medical Monitor. The Day 1 (baseline and randomization) visit occurs on the first day of study drug administration.

At applicable sites (United States only), if the patient is unable to return to the clinic at the Week 24 visit for the PK blood draw at the 8- to 10-hour timepoint, then this sample may be collected by a home nurse (HN) professional at the patient's home or another suitable location to improve access and convenience for patients participating in the study. The Sponsor will select a healthcare company that will be responsible for

providing HN services for participating sites (the HN vendor). The HN vendor is responsible for ensuring that all HN professionals are licensed, qualified, and in good standing, as per applicable regulations, and that appropriate background checks have been performed. If the investigator at a participating site determines that HN services are appropriate for a patient and the patient gives written informed consent to participate in HN visits, the HN network will communicate with the patient and the patient's site. HN visits will be scheduled on specified visit days, to allow for relevant assessments to be performed by the HN professional. The schedule of activities will specify the assessments that may be performed by an HN professional (see [Appendix 1](#) and [Appendix 2](#)).

#### **4.5.1 Informed Consent Forms and Screening Log**

Patients will be screened within a period of up to 35 days prior to administration of study medication to confirm that they meet the entrance criteria for the study. The study investigator or sub-investigator will discuss with each patient the nature of the study, its requirements, and its restrictions and potential risks.

Written informed consent for participation in the study must be obtained before performing any study-related procedures. Informed Consent Forms for enrolled patients and for patients who are not subsequently enrolled will be maintained at the study site.

All screening evaluations must be completed and reviewed to confirm that patients meet all eligibility criteria before enrollment. Pre-enrollment adjudication by the Medical Monitor and his/her designees will occur for all patients who complete screening prior to their randomization into the study (see [Appendix 3](#)). The investigator will maintain a screening log to record details of all patients screened and to confirm eligibility or record reasons for screening failure, as applicable.

#### **4.5.2 Eligibility Assessment at Screening**

At screening, patients who fail to meet any laboratory inclusion/exclusion criteria or other eligibility criteria may be retested or rescreened per the instructions in [Section 4.5.2.1](#) and [Section 4.5.2.2](#), respectively.

##### **4.5.2.1 Re-Testing: Laboratory Inclusion/Exclusion**

If a patient fails certain laboratory inclusion/exclusion criteria at screening, the investigator may repeat the test once within the screening period; see [Section 4.1.2](#) for a list of laboratory tests and levels that can be retested. If the patient passes the laboratory eligibility criteria on the second assessment, he/she will be adjudicated and may enter the study. It will not be considered a re-testing if blood samples have to be redrawn due to sample handling problems, breakage, sample integrity, or laboratory error.

#### **4.5.2.2 Re-Screening**

Re-screening refers to repeating the whole screening process. Re-screening is required if a patient has not met all of the eligibility criteria within the original screening period (Note: patients who have failed two laboratory testing attempts as described in Section 4.5.2.1 cannot be re-screened). Patients are only allowed to be re-screened once. Each patient must be re-consented before re-screening occurs. It will not be considered a re-screening if blood samples have to be redrawn due to sample handling problems, breakage, sample integrity, or laboratory error.

#### **4.5.3 Medical History and Demographic Data**

A complete medical history will be taken at the screening visit and should include details of past and current manifestations of SLE, past and current concomitant medical conditions, previous surgical procedures, and previous treatment regimens for SLE including any history of adverse drug reactions. In addition, all medications (e.g., prescription drugs, over-the-counter drugs, vaccines, herbal or homeopathic remedies, nutritional supplements) used by the patients within 7 days prior to screening will be recorded.

Particular emphasis should be placed on manifestations of active SLE as well as the clinical and laboratory findings that identified the patient as having SLE (ACR or SLICC criteria) and on identifying any medical conditions (e.g., active or latent infection) that might place the patient at increased risk or which might confound the interpretation of safety or efficacy signals. At subsequent visits, the investigator will focus on changes in the patient's symptoms since the previous visit, including but not limited to features indicating current SLE activity, changes in disease activity since the previous visit, and potential adverse events.

The medical history must also include clinically significant diseases, surgeries, cancer history (including prior cancer therapies and procedures), reproductive status, family history of autoimmunity, vaccine history, smoking history, use of alcohol, and drugs of abuse.

A detailed history of medication used for SLE is required. All prior immunosuppressant drugs used to treat lupus 12 months prior to screening (including drug name, maximum dose used, and start and stop dates, as applicable) will be recorded. The year of onset as well as the symptoms that lead to the diagnosis of SLE in the patient as defined by either the ACR or SLICC inclusion criteria should be captured.

Demographic data will include age, sex, and self-reported race/ethnicity.

#### **4.5.4 Physical Examinations**

A complete physical examination should be performed at screening and should include an evaluation of the head, eyes, ears, nose, and throat, and the cardiovascular, dermatological, musculoskeletal, respiratory, GI, genitourinary, and neurological systems.

Any abnormality identified at baseline should be recorded on the General Medical History and Baseline Conditions eCRF. Particular attention should be given to evaluation of potential manifestations of active SLE and of infections or other medical conditions, which could place the patient at increased risk.

At subsequent visits (or as clinically indicated), limited, efficacy assessment–directed or symptom-directed physical examinations should be performed. Changes from baseline abnormalities should be recorded in patient notes. New or worsened clinically significant abnormalities should be recorded as adverse events on the Adverse Event eCRF.

#### **4.5.5 Vital Signs**

Vital signs will include measurements of respiratory rate, pulse rate, temperature, and systolic and diastolic blood pressures while the patient is in a seated position for at least 5 minutes.

#### **4.5.6 Chest Radiograph**

Chest radiographs of appropriate quality (to adhere to local standards for the exclusion of active TB) and with formal readings by a radiologist will be obtained at screening. If chest radiographs have been taken and read by a radiologist within 12 weeks prior to screening and documented results (as read by a radiologist) show no clinically significant abnormality as determined by the investigator, the chest radiograph does not need to be repeated.

#### **4.5.7 Tuberculin Purified Protein Derivative Skin Test**

The QuantiFERON TB-Gold® (QFT) should be used as the initial screening test for tuberculosis and, if indeterminate, this QFT test should be followed by a repeat QFT or a T-SPOT® test. If QFT is not available, a Mantoux PPD skin test will be performed at the screening visit or within the 12 weeks prior to screening and read locally. The PPD skin test will be performed per the CDC guidelines using 5 tuberculin units per 0.1 mL [5TU]. An intradermal injection into flexor or dorsal surface of forearm will be performed.

#### **4.5.8 SLE Disease Activity Assessments**

The following applicable SLE disease activity assessments will be used in this study: BILAG-2004, SLEDAI-2K, SELENA-SLEDAI Flare Index (SFI), Glucocorticoid Toxicity Change Index [GTCI], SLICC/ACR *Damage Index (SDI)*, 28-Joint Count, CLASI, Physician's Global Assessment, and Patient's Global Assessment. In addition, the SRI and BICLA composite endpoints will be evaluated. Throughout the study, each assessment ideally should be conducted by the same assessor, if possible (e.g., the same assessor should conduct the 28-joint count at each visit for a particular patient, if possible). Detailed instructions and training on the use of clinical instruments performed by the investigators in this study will be provided by the Sponsor or Sponsor designee. Investigators must demonstrate the ability to perform disease activity assessments

and/or they must provide valid training certificates obtained within 2 years of the start of the study for versions used in this study.

#### **4.5.8.1 BILAG 2004 Index**

The BILAG 2004 index (BILAG) will be used as a method to assess disease activity in this study.

The BILAG assesses 97 clinical signs, symptoms, and laboratory parameters across nine organ or system domains: constitutional, mucocutaneous, neuropsychiatric, musculoskeletal, cardiorespiratory, GI, ophthalmic, renal, and hematological. The 97 symptoms are rated with respect to severity over the previous month (4 weeks) and with respect to any change from the previous examination (new, improving, stable, worsening, absent). For each of the nine domains, a single, alphabetic score (i.e., A through E) is then derived from the examination results in each organ category.

Detailed instructions and training on the use of the BILAG will be provided as described in [Appendix 9](#).

#### **4.5.8.2 Systemic Lupus Erythematosus Disease Activity Index 2000 (SLEDAI-2K) and SELENA-SLEDAI Flare Index (SFI)**

The SLEDAI-2K will be used to approximate disease activity for entry into the study and at every subsequent study visit (see [Appendix 10](#)).

SLEDAI-2K measures disease activity at the visit or within the preceding 28 days. Detailed instructions and training on the use of the SLEDAI-2K will be provided during training sessions at each investigator meeting, and through online resources. It is critical that investigators have a thorough understanding of both *the BILAG and SLEDAI-2K* instruments and the differences between them.

The SFI categorizes SLE flare as “mild or moderate” or “severe” based on 6 variables ([Buyon et al, 2005](#); [Petri et al. 1999](#); [Petri et al. 2005](#)):

- Change in SELENA-SLEDAI (or SLEDAI-2K) score from the most recent assessment to current
- Change in signs or symptoms of disease activity
- Change in prednisone dosage
- Use of new medications for disease activity or hospitalization
- Change in PGA score
- Hospitalization for activity (severe flare only)

The *SFI* will be modified such that severe flares *defined only by the occurrence of an increase in SLEDAI-2K score to > 12* will be excluded. One or more other items defining severe flare in the SFI needed to be present for a severe flare to be recorded. This modification was made because patients entering the trial with high disease activity

(e.g.,  $\geq 11$ ) could too easily trigger a severe flare by minor increases in the SLEDAI-2K score.

#### **4.5.8.3 Glucocorticoid Toxicity Change Index**

The GTCI is an exploratory standardized measure of damage related to use of glucocorticoids (see [Appendix 12](#)). The GTCI will be incorporated into this study to better quantify the accrual of damage linked to corticosteroid use in patients with lupus and may allow for an improved understanding of standard of care and patient phenotype.

#### **4.5.8.4 Systemic Lupus International Collaborating Clinics (SLICC)/ACR Damage Index for Systemic Lupus Erythematosus**

The SLICC/ACR Damage Index (*SDI*) for SLE will be utilized to assess organ damage as opposed to the collection of disease activity (see [Appendix 7](#)). Damage is defined as non-reversible change not related to active inflammation.

#### **4.5.8.5 28-Joint Count**

For all patients, 28-joint counts should be performed at the intervals specified in the Schedule of Activities (see [Appendix 1](#)). The joint counts must be performed by an assessor with experience in performing these assessments; this may be the Principal Investigator, subinvestigator, or another trained individual approved by the Sponsor. The joint counts on a given patient *are strongly recommended* to be performed by the same assessor, whenever possible, at each study visit.

The 28 joints included in this assessment are listed in [Appendix 13](#).

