**Table 1 Objectives and Corresponding Endpoints (cont'd)**

Objectives	Corresponding Endpoints
Exploratory Efficacy Objectives (cont'd):	

 
To evaluate the ability of GDC-0853 to prevent systemic damage
 
	
 
Change in SLICC/ACR Damage Index at Week 24 and Week 48 relative to baseline
 

 
To evaluate the ability of GDC-0853 to improve arthritis
 
	
 
Change in joint involvement at Week 24 and Week 48 relative to baseline using the 28-Joint Count assessment
 
≥ 50% improvement in the 28 Joint Count assessment for patients with ≥ 8 swollen or tender joints at baseline
 

 
To evaluate the ability of GDC-0853 to improve fatigue
 
	
 
Change in FACIT-Fatigue score at Week 24 and Week 48 relative to baseline
 

 
To evaluate the ability of GDC-0853 to improve Patient's Global Assessment
 
	
 
Change in Patient's Global Assessment of disease activity at Week 24 and Week 48 relative to baseline
 

 
To evaluate if GDC-0853 is steroid sparing
 
	
 
Change in cumulative steroid dose at Week 24 and Week 48 relative to baseline
 
Glucocorticoid toxicity at Weeks 12, 24, 36, and 48 relative to baseline using the GTCI
 
Achieving a corticosteroid dose of < 10 mg/day among patients at ≥ 10 mg/day at baseline
 

Safety Objective:	

 
To evaluate the safety of GDC-0853 in combination with SOC therapy in patients with moderate to severe active SLE
 
	
 
The nature, frequency, severity, and timing of adverse events using the NCI CTCAE scale to grade adverse events
 
Changes in vital signs, physical findings, ECGs, and clinical laboratory results following GDC-0853 administration
 

Pharmacokinetic Objective:	

 
To characterize the pharmacokinetics of GDC-0853 in patients
 
	
 
Plasma concentrations of GDC-0853 at specified timepoints
 

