### **6.4.3 Exploratory Efficacy Endpoints**

The exploratory efficacy endpoints are as follows:

- *SRI-5, 7, and 8 response at Weeks 24 and 48*
- *SRI-5-8 response at Week 48 with a sustained reduction of OCS dose to < 10 mg/day and ≤ Day 1 dose during Week 36 through Week 48*
- *SRI-5-8 response at Week 24 with a sustained reduction of OCS dose to < 10 mg/day and ≤ Day 1 dose during Week 12 through Week 24*
- Time to first SLE flare as defined by the SFI
- Time to first SLE flare as defined by the BILAG
- Total number of SLE flares as defined by the SFI
- Total number of SLE flares as defined by the BILAG
- *Reduction of ≥ 4 points from baseline in the SLEDAI-2K at Weeks 24 and 48*
- *SRI-4 response at Week 24 in patients with high plasmablast signature levels relative to patients with low levels*
- *SRI-4 response at Week 24 with a sustained reduction of OCS dose to < 10 mg/day and ≤ Day 1 dose during Week 12 through Week 24 in patients with high plasmablast signature levels relative to patients with low levels*
- Change in CLASI Total Activity Score at Week 24 and Week 48 relative to baseline
- ≥50% improvement in CLASI score in patients with at least moderate skin involvement (baseline CLASI ≥10)
- Change in SLICC/ACR Damage Index at Week 24 and Week 48 relative to baseline
- Change in joint involvement at Week 24 and Week 48 relative to baseline
- ≥50% improvement in swollen or tender joint count (28 joints) for patients with ≥8 swollen or tender joints at baseline
- Change in FACIT-Fatigue score at Week 24 and Week 48 relative to baseline
- Change in Patient's Global Assessment of disease activity at Week 24 and Week 48 relative to baseline
- Change in cumulative steroid dose use at Week 24 and Week 48 relative to baseline
- Glucocorticoid toxicity at Weeks 12, 24, 36, and 48 relative to baseline using the GTCI
- *Achieving* corticosteroid dose of < 10 mg/day among patients with a dose ≥ 10 mg/day at baseline

Exploratory endpoints will be evaluated for the ITT population. Time-to-event endpoints will be analyzed using the Kaplan-Meier methodology. Continuous endpoints will be analyzed using an appropriate analysis method, such as analysis of covariance, or

mixed-model repeated measures. Categorical endpoints will be analyzed using an appropriate statistical method, such as Cochran-Mantel-Haenszel or Fisher's exact test.

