## Appendix 1 Schedule of Activities (cont.)

Study Week	Screen –35 Days a		Treatment														SFU	UV d	FV e	ET	
	1 st visit	2 nd visit	0 b	1	4	8	12	16	20	24 b	28	32	36	40	44	48 c	56				
Day (Visit Window)			1	8 (±1)	29 (±3)	57 (±3)	85 (±3)	113 (±3)	141 (±3)	169 (±3)	197 (±5)	225 (±5)	253 (±5)	281 (±5)	309 (±5)	337 (±5)	393 (±5)				
(U.S. sites only) tr, nn																					
BILAG 2004	X		X		X	X	X	X	X	X	X	X	X	X	X	X	X	X	X	X	X
SLEDAI-2K and SFI	X		X		X	X	X	X	X	X	X	X	X	X	X	X	X	X	X	X	X
GTCI and fasting lipids oo			X				X			X			X			X					
SLICC/ACR damage index			X							X						X					
28-Joint Count & morning stiffness pp	X		X		X	X	X	X	X	X	X	X	X	X	X	X	X	X	X	X	X
CLASI	X		X		X		X			X			X			X	X	X	X	X	X
Optional photographic documentation (U.S. sites only) qq	X		X		X		X			X			X			X	X	X	X	X	X
Physician Global Assessment rr	X		X		X	X	X	X	X	X	X	X	X	X	X	X	X	X	X	X	X
Patient Global Assessment ss	X		X		X	X	X	X	X	X	X	X	X	X	X	X	X	X	X	X	X
FACIT-Fatigue Scale ss			X				X			X			X			X	X		X		
Study drug administration in clinic tt			X		X					X											
Drug dispensing			X		X	X	X	X	X	X	X	X	X	X	X						
Blood for WGS qq			X																		
Blood for serum for RBR (optional)	X		X				X			X						X			X		

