## Appendix 1 Schedule of Activities (cont.)

- ff Collect prior to drug administration.
- gg Collect PK samples at four timepoints: prior to study drug, 2 hours ( $\pm$  30 minutes) post-dose (fasting), 4–6 hours post-dose, and 8–10 hours post dose (U.S. sites only). If the patient is unable to stay or return to clinic for the post-dose 8-10 hour timepoint, this sample may be collected by a home nurse visit.
- hh Sample to be collected at baseline. However, if sample not drawn at baseline, it may be collected at any other timepoint.
- ii Three PaxGene whole blood tubes to be collected prior to study drug administration for PD sample. Please see laboratory manual for PaxGene blood sample handling.
- jj Collect serum and plasma tubes prior to study drug administration for PD biomarker serum and PD biomarker plasma.
- kk *U.S. sites only*: Blood for PBMCs will be shipped overnight to a central laboratory for processing. To be performed at centers where samples can be shipped to central laboratory within 24 hours.
- ll *U.S. and selected sites only*: Includes multi-color flow cytometry analysis of B cells and B cell subsets
- mmm Includes multi-color flow cytometry analysis of basophil activation. To be performed at centers in the United States where samples can be shipped to FACS laboratory within 24 hours.
- nn *U.S. sites only*: Blood for PBMCs will be shipped overnight to a central laboratory for processing and cryopreserved. To be performed at centers where samples can be shipped to central laboratory within 24 hours.
- oo Fasting lipid panel includes triglycerides, HDL, LDL, HbA1c, and total cholesterol. The patient should be fasting ( $\geq$  4 hours).
- pp For patients with arthritis present at current visit prior to Week 24 or any past visit during the study.
- qq WGS and photography are contingent upon the review and approval by each site's IRB/EC and, if applicable, an appropriate regulatory body.
- rr The same clinician *is strongly recommended to* complete the Physician's Global Assessment throughout the study.

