## **Appendix 13 28-Joint Count**

The number of tender joints and the number of swollen joints will be assessed on any patient in whom arthritis is present at the current visit or in whom arthritis has been present at any previous visit during the study.

The joint counts must be performed by an assessor with experience in performing these assessments; this may be the Principal Investigator, subinvestigator, the study coordinator, or another trained individual approved by the Sponsor. The joint counts on a given patient should be performed by the same assessor at each study visit.

The 28 joints to be assessed for tenderness and swelling are as follows:

- Shoulders (2 joints)
- Elbows (2 joints)
- Wrists (2 joints)
- Interphalangeal of each thumb (2 joints)
- Proximal interphalangeal joints on fingers 2–5 (8 joints)
- Metacarpophalangeal joints on digits 1–5 (10 joints)
- Knees (2 joints)

The choice of joints included in this assessment is based on the 28-joint count performed as part of the Disease Activity Score (DAS)-28 for assessment of disease activity in rheumatoid arthritis.

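### Three different rules say who gets a 28-joint count; under the Appendix 1 footnote, arthritis first seen at Week 24 or Week 48 goes uncounted at that endpoint visit, and under both appendices some patients have no baseline count

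*Combined protocol and SAP*

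**What the plan says.** Three places in the protocol define who receives the 28-joint count.

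- Section 4.5.8.5: "For all patients, 28-joint counts should be performed at the intervals specified in the Schedule of Activities".
- Appendix 1, the row "28-Joint Count & morning stiffness", which is marked at screening, at each clinic visit from Week 0 to Week 48, and at the follow-up, unscheduled, flare and early termination visits. The row carries footnote pp: "For patients with arthritis present at current visit prior to Week 24 or any past visit during the study".
- Appendix 13: tender and swollen joints are "assessed on any patient in whom arthritis is present at the current visit or in whom arthritis has been present at any previous visit". It has no Week 24 condition.

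Two exploratory endpoints use the count. Table 1 lists "Change in joint involvement at Week 24 and Week 48 relative to baseline using the 28-Joint Count assessment". Section 6.4.3 lists at least a "50% improvement in swollen or tender joint count (28 joints) for patients with" 8 or more such joints at baseline. Section 6.4.3 adds: "Exploratory endpoints will be evaluated for the ITT population". The opening of Section 6 leaves instrument scoring and missing-data handling to the Data Analysis Plan (DAP), which is not among the documents available.

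**The concern.** A site cannot follow all three rules. The body text points to the schedule for timing, and the schedule then narrows the population through a footnote.

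Change from baseline needs a count at Day 1 and a count at Week 24 or Week 48. A rule that starts counting only once arthritis has appeared removes the first value in patients who develop it later. A rule that also excludes arthritis first seen from Week 24 on can remove the second value at the two visits where the endpoint is read. Whether a count is missing then depends on the patient's joint status, so the gaps are not random. A count not done at a visit cannot be recovered afterwards.

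**Working it through.** There is no stated figure to reproduce and no power or error-rate calculation applies. The check sets the three rules side by side and follows each type of patient through the schedule.

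**Visits.** Clinic visits run every 4 weeks from Week 0 to Week 48: 48/4 + 1 = 13. Those not before Week 24 number (48 − 24)/4 + 1 = 7. Two of the seven are endpoint visits (Weeks 24 and 48) and five are not (Weeks 28, 32, 36, 40 and 44).

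**Is the count done?**

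| Situation | Section 4.5.8.5 | Footnote pp | Appendix 13 |
|---|---|---|---|
| No arthritis at screening or Day 1: Day 1 count | Yes | No | No |
| Arthritis at screening but not Day 1: Day 1 count | Yes | Yes | Yes |
| First seen at Weeks 4 to 20: count at that visit | Yes | Yes | Yes |
| First seen at Week 24: count at Week 24 | Yes | No | Yes |
| First seen at Weeks 28 to 44: count at that visit | Yes | No, starts at next visit | Yes |
| First seen at Week 48: count at Week 48 | Yes | No | Yes |
| Arthritis at any earlier visit: counts at Weeks 24 and 48 | Yes | Yes | Yes |
| Never arthritis: counts at Weeks 24 and 48 | Yes | No | No |

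The second row treats screening as a visit during the study, since the joint-count row is marked there.

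**Effect on the endpoint.** Write the change at week t as C(t) − C(0).

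- Under either appendix, C(0) is not measured in anyone without arthritis at screening or Day 1. If arthritis appears later, no change can be calculated from measured values, even where C(24) or C(48) exists.
- Under footnote pp, C(24) is also missing when arthritis is first seen at Week 24, and C(48) when it is first seen at Week 48.
- If the DAP set an unmeasured C(0) to zero, the change could be calculated wherever a follow-up count exists. The two follow-up gaps under footnote pp would remain. Setting those to zero as well would record a patient with new arthritis as unchanged.
- Zero is not certain to be right at baseline. Neither footnote pp nor Appendix 13 defines arthritis, and the SLEDAI-2K item in Appendix 10 needs at least two affected joints, so a patient with one tender joint could be classed as having none.

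**Can patients enter without arthritis?** Yes. Section 4.1.1 asks for a SLEDAI-2K score of at least 8 at screening with a clinical score of at least 4. In Appendix 10, rash, alopecia, mucosal ulcers and pleurisy score 2 + 2 + 2 + 2 = 8 with no arthritis item.

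**The second joint endpoint.** Patients with 8 or more swollen or tender joints at baseline would mostly have arthritis on Day 1 and be counted under all three rules. The exception is a patient whose tender joints are not called arthritis.

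**The case against.** The strongest reply is that this is a wording mismatch with narrow reach. Most of that stands, and it rules out several stronger readings.

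- A reader might infer that joint counts stop at Week 24. They do not. The Week 24 condition applies only to the current-visit trigger. Past arthritis keeps a patient in the count through Week 48, and Appendix 13 has no such condition.
- A reader might infer that new arthritis goes unrecorded. SLEDAI-2K and BILAG are scheduled at every clinic visit and both record arthritis. What is lost is the number of joints.
- A reader might infer that everyone without Day 1 arthritis lacks a baseline. Arthritis at screening is enough to require a Day 1 count under both appendices.
- A reader might infer that worsening is hidden more in the arm with more flares. That would follow only if the arms differed in arthritis first appearing at the visits concerned. The documents give nothing to show this or to size it.

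It can also be argued that conditional counting was intended. Section 4.5.8.6 limits the CLASI to patients with mucocutaneous disease, and Appendix 15 mentions joint counts as done where appropriate. If so, Section 4.5.8.5 is the passage in error, but the Week 24 gap and the absent baseline remain. The DAP may contain a baseline rule. It could not supply a follow-up count that was never made.

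**Conclusion.** The three passages contradict each other. Followed as written, footnote pp loses the joint count for arthritis first seen at Week 24 or Week 48 at that endpoint visit, and delays by one visit the first count for arthritis first seen at Weeks 28 to 44. Both appendices leave patients with no arthritis at screening or Day 1 without a measured baseline. These losses arise only where sites follow the appendices rather than the body text.

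This is a minor point. It bears on the exploratory change in joint involvement and barely on the subset with at least 8 joints at baseline. It does not reach SRI-4, SRI-6 or BICLA, none of which includes the joint count. Section 6.4 already treats positive tests as hypothesis generating. The number of patients affected cannot be estimated, because the documents give neither the share entering without arthritis nor the rate of first arthritis at particular visits.

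**What to change.** Adopt one rule in all three places. The simplest is to make footnote pp and Appendix 13 match Section 4.5.8.5, so that every patient has a 28-joint count at every scheduled visit.

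If conditional counting is preferred between endpoint visits, the minimum is:

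- delete the words *prior to Week 24* from footnote pp;
- require a Day 1 count in all patients;
- require a count in all patients at Weeks 24 and 48;
- change Section 4.5.8.5 and Appendix 13 to state the same rule.

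Under either option, the DAP should say how a patient without a baseline count is handled, since some may already have been enrolled under the footnote.

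The cost is a change of wording and a short added count in patients without arthritis. Appendix 1 footnote m already requires an examination at these visits sufficient to complete SLEDAI-2K and BILAG, both of which include arthritis.
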